## **10.0 Safety Analyses**

### **10.1 General Considerations**

Safety summaries will be provided using the safety Populations. For the safety analysis, subjects are assigned to a treatment group based on the treatment actually received, regardless of the treatment randomized.

Safety analyses will include adverse events, laboratory, and vital sign measurements. Missing safety data will not be imputed.

### **10.2 Adverse Events**

The summaries of adverse events will be provided by treatment groups (defined in [Table 1](#)) in Period 1 for Safety 1 Population, in Period 2 for Safety 2 Population, and during the administration of upadacitinib for All UPA Population.

### 10.2.1 Treatment-Emergent Adverse Events

Treatment-emergent adverse events (TEAEs) are defined as follows:

- TEAEs in Period 1 are defined as any adverse events that begin or worsen in severity after initiation of upadacitinib/dupilumab through the minimum (30 days following the last dose of upadacitinib in Period 1 or through 84 days following the last dose of dupilumab in Period 1, the start day of Period 2 – 1).
- TEAEs in Period 2 are defined as any adverse events that begin or worsen in severity after initiation of upadacitinib in Period 2 through 30 days following the last dose of upadacitinib in Period 2.
- TEAEs during the administration of upadacitinib are defined as any adverse events that begin or worsen in severity after initiation of upadacitinib through 30 days following the last dose of upadacitinib.

If a missing or an incomplete onset date is collected for an adverse event, the event will be assumed to be treatment-emergent unless there is other evidence that confirms that the event is not treatment-emergent (e.g., the event end date is prior to the study drug start date). Events where the onset date is the same as the study treatment start date are assumed to be treatment-emergent. All treatment-emergent AEs will be summarized overall, as well as by primary MedDRA SOC and Preferred Term. The SOCs will be presented in alphabetical order, and the PTs will be presented in alphabetical order within each SOC.

The number and percentage of subjects experiencing TEAEs and the number of events per 100 patient-years of exposure will be summarized.

TEAEs per 100 patient-years of exposure are defined as the number of TEAEs divided by the total exposure in 100 patient-years. See the calculation method below:

$$100 * (\text{Number of TEAEs}) / (\text{Total Patient Years})$$

where total patient years is defined as the sum of the study drug duration (defined in Section 6.0) of all subjects normalized by 365.25 and rounded to 1 decimal place.

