- **Upadacitinib arm (N = 440):** Daily oral doses of upadacitinib 15 mg QD from the Baseline visit until the Week 16 visit. During Period 1, subjects randomized to upadacitinib 15 mg QD will have their dose increased to 30 mg QD if any of the following parameters is met:
 - Starting at Week 4, subject has a < EASI 50 response
 - Starting at Week 4, subject has a < 4-point improvement from Baseline in WP-NRS (weekly average)
 - Starting at Week 8, subject has a < EASI 75 responseAt Week 16, subjects receiving upadacitinib 15 mg QD or 30 mg QD, will be reassigned based on their EASI response:
 - < EASI 75 will be allocated or continue to receive oral doses of upadacitinib 30 mg QD in Period 2
 - ≥ EASI 75 will complete end of study procedures.
- **Dupilumab arm (N = 440):**
 - Adults: Dupilumab 600 mg (2 × 300 mg dupilumab SC injection) administered at the Baseline visit, followed by dupilumab 300 mg SC injection EOW until the Week 16 visit.
 - Adolescents: Adolescents (12 to 17 years of age and weighing at least 40 kg).

Dose of dupilumab for subcutaneous administration in adolescent patients 12 to 17 years of age with AD.

Body weight of subject at Screening Visit and at each visit:

1. 40 to < 60 kg:
 - Initial dose: 400 mg (two 200 mg injections)
 - Subsequent doses (EOW): 200 mg
2. 60 kg or more:
 - Initial dose: 600 mg (two 300 mg injections)
 - Subsequent doses (EOW): 300 mg
- At Week 16, subjects receiving dupilumab as per its label will be reassigned based on their EASI response:
 - < EASI 75 will be offered the option to receive oral doses of upadacitinib 15 mg QD and enter Period 2
 - \geq EASI 75 will complete end of study procedures
- During Period 2, subjects randomized to upadacitinib 15 mg QD will have their dose increased to 30 mg QD if any of the following parameters is met:
 - Starting at Week 20, subject has a < EASI 75 response
 - Starting at Week 20, subject has a < 4-point improvement from Baseline in WP-NRS (weekly average)

An unscheduled visit may be used for this purpose if necessary for dose escalation.

Any subject treated for at least 8 weeks with upadacitinib 30 mg QD with a < EASI 50 response (reduction from Baseline) after rescue with topical corticosteroid treatment for at least 1 week must be discontinued.

[figure not shown]

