## **2.0 Study Objectives and Design**

### **2.1 Study Objectives, Hypotheses and Estimands**

The primary study objective, related to Study Period 1, is to assess the efficacy and safety of upadacitinib, initiated at 15 mg once daily (QD) and dose adjusted based on clinical response, compared with dupilumab as per its label. An additional objective, related to Study Period 2, is to assess the efficacy and safety of upadacitinib, initiated at 15 mg QD and dose adjusted based on clinical response, in subjects with inadequate response to dupilumab and treated at 30 mg QD in subjects with inadequate response to upadacitinib in Period 1. The primary efficacy objective is based on the achievement of an at least 90% reduction in EASI from baseline (EASI 90) and a Worst Pruritus Numerical Rating Scale of 0 or 1 (WP-NRS 0/1) at Week 16 with the treatment of upadacitinib compared with dupilumab in the Intent-to-Treat (ITT) Population, which consists of all randomized

subjects. The secondary efficacy objectives are based on ranked secondary endpoints as defined in Section 3.2 (below) with the treatment of upadacitinib compared with dupilumab in the ITT Population.

The hypothesis corresponding to the primary efficacy endpoint (Section 3.1) is:

The proportion of subjects achieving EASI 90 and WP-NRS 0/1 at Week 16 in those treated with upadacitinib is greater than those treated with dupilumab.

The estimand corresponding to the primary endpoint is defined using the composite variable strategy, as follows:

Difference in the proportion of subjects achieving EASI 90 and WP-NRS 0/1 at Week 16 without the use of rescue medication between upadacitinib and dupilumab in the adolescents and adult subjects with moderate to severe AD who have inadequate response to systemic therapy.

The hypotheses and estimands corresponding to the ranked secondary endpoints are summarized below.

Hypotheses: the proportion of subjects achieving each ranked endpoint in those treated with upadacitinib is greater than those treated with dupilumab.

Estimands: Difference in proportion of subjects achieving each of ranked secondary endpoints without the use of rescue medication between upadacitinib and dupilumab in adolescents and adult subjects with moderate to severe AD who have inadequate response to systemic therapy.

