response to dupilumab and treated at 30 mg QD in subjects with inadequate response to upadacitinib in Period 1. At Week 16 subjects from both treatment arms with a < EASI 75 response will enter Period 2; subjects from the dupilumab arm will be offered the option to receive upadacitinib 15 mg QD while subjects from the upadacitinib arm will either continue (if already receiving 30 mg) or be escalated to upadacitinib 30 mg QD (if receiving 15 mg QD) until Week 32.

The details for Upadacitinib/Dupilumab arms and the dose adjustment for each treatment arm in each study period can be found in Protocol Section 4.1.

[figure not shown]
The primary analysis for the study will be performed when all ongoing subjects have completed Week 16 or permanently discontinued Period 1, and all data pertaining to Period 1 are cleaned. This analysis is the final and only analysis for the primary and ranked secondary endpoints. Additional analyses may be performed as appropriate.

The schematic of the study is shown in [Figure 1](#).

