## 10.2.2 Adverse Event Overview

The number and percentage of subjects experiencing TEAEs will be summarized for each treatment group for the following AE categories.:

- Any TEAE
- Any treatment-emergent serious adverse events (SAE)
- Any TEAE leading to discontinuation of study drug
- Any severe TEAE (Grade 3 and above according to National Cancer Institute (NCI) Common Terminology Criteria for Adverse Events (CTCAE) version 5.0)
- Any TEAE related to study drug according to the investigator
- Any treatment-emergent SAE related to study drug according to the investigator
- TEAEs of Special Interest
- Other Safety Topics of Interest
- Any TEAE leading to death
- All Deaths
  - Deaths occurring  $\leq$  30 days after last dose of upadacitinib or  $\leq$  84 days after last dose of dupilumab
  - Deaths occurring  $>$  30 days after last dose of upadacitinib or  $>$  84 days after last dose of dupilumab
  - Related to COVID-19

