### **10.2.6 Adverse Events of Special Interest**

Adverse events of special interest will be summarized by SOC and PT and listing format and will be based on standard or company MedDRA queries (SMQs or CMQs) 1) from Baseline to Week 16 visit and 2) the entire upadacitinib treatment period, respectively.

Adverse events of special interest are categorized as follows:

- Serious infections
- Opportunistic infections excluding tuberculosis and herpes zoster
- Herpes Zoster
- Active Tuberculosis
- Anemia
- Neutropenia
- Lymphopenia
- Renal Dysfunction
- Hepatic disorder
- Creatine Phosphokinase Elevations (CPK; adolescents only)
- Possible Malignancy\*
- Malignancy
- Non-melanoma skin cancer (NMSC)
- Malignancy excluding NMSC
- Lymphoma
- Adjudicated MACE
- Adjudicated VTE
- Adjudicated gastrointestinal perforations

\* Possible Malignancy is used for surveillance and safety monitoring for both clinical trial and post marketing data and will not be included as AESI in in text tables for any safety document.

Detailed information about the search criteria is provided in [Appendix B](#).

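### For subjects who do not enter Period 2, Period 1 TEAEs are counted to about Day 142 on upadacitinib but about Day 183 on dupilumab, and neither the percentages nor the patient-year rates correct for it

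*SAP*

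**What the plan says.** The Period 1 window in SAP 10.2.1 opens at first dose and closes at a minimum of two dates. The first date depends on the drug: "30 days following the last dose of upadacitinib in Period 1", or "through 84 days following the last dose of dupilumab in Period 1". The second is the day before "the start day of Period 2". Protocol 7.5 gives the same 30 and 84 days and ties them to five half-lives.

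Period 2 entry depends on Week 16 response: "At Week 16 subjects from both treatment arms with a < EASI 75 response will enter Period 2". For the dupilumab arm this is an offer, so some eligible subjects may decline.

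SAP 10.2.2 reports on this window: "The number and percentage of subjects experiencing TEAEs will be summarized for each treatment group for the following AE categories". SAP 10.2.3 does the same by system organ class and preferred term. SAP 10.2.1 and 10.2.4 add events per 100 patient-years, with patient-years taken from the study drug duration in SAP 6.0. The AESI summaries in SAP 10.2.6 use other windows: "1) from Baseline to Week 16 visit and 2) the entire upadacitinib treatment period, respectively".

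Safety is part of the comparison with dupilumab in the primary objective: "The primary study objective, related to Study Period 1, is to assess the efficacy and safety of upadacitinib" (SAP 2.1).

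**The concern.** A percentage of subjects with an event grows with the time over which events are counted. If one arm is counted for longer, it shows more subjects with events even when the drugs carry the same risk. Here the counting time differs by arm for everyone who does not enter Period 2, including subjects who stop early and keep the 30- or 84-day tail. It also differs within an arm by Period 2 entry, which follows from Week 16 EASI response. That response is a post-randomisation outcome which the trial expects to differ between arms. A reader comparing the two columns of the TEAE overview could not tell drug effect from window length, and no planned table for any TEAE, SAEs, severe TEAEs or the SOC/PT rows uses a common window.

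**Working it through.** The plan states no total window length and no expected TEAE rate, so there is no plan figure to reproduce. Everything about size below rests on assumptions.

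**Inputs from the documents**
- Upadacitinib: "Daily oral doses of upadacitinib 15 mg QD from the Baseline visit until the Week 16 visit" (Protocol 4.1). The Week 16 visit is Day 113, so the last Period 1 dose is about Day 112.
- Dupilumab: SAP 6.0 makes Week 14 the last planned dose, which is Day 1 + 14 × 7 = Day 99.
- Tails: 30 and 84 days. Cap: the day before Period 2, about Day 112.

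**Windows**
- Not entering Period 2: upadacitinib 112 + 30 = Day 142; dupilumab 99 + 84 = Day 183. The gap is 41 days and the ratio 183/142 = 1.29.
- Entering Period 2: about Day 112 in both arms.

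**Patient-year rates (SAP 6.0 durations)**
- Upadacitinib completer: 112 − 1 + 1 = 112 days.
- Dupilumab completer: 99 − 1 + 14 = 112 days.
- Events are counted over 142 or 183 days against the same 112. With equal risk, the rates are inflated by 142/112 = 1.27 and 183/112 = 1.63, and their ratio is 1.29.

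**Percentages.** Assume the same constant hazard in both arms, complete follow-up, and Period 2 entry unrelated to adverse event risk. Let p be the risk by Day 112, so P(d) = 1 − (1 − p)^(d/112). With a share f entering Period 2:

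- upadacitinib % = f_u · P(112) + (1 − f_u) · P(142)
- dupilumab % = f_d · P(112) + (1 − f_d) · P(183)

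For p = 50%, P(142) = 58.5% and P(183) = 67.8%. With 20% and 40% entering:
- upadacitinib 0.2 × 50 + 0.8 × 58.5 = 56.8%
- dupilumab 0.4 × 50 + 0.6 × 67.8 = 60.7%
- difference 3.9 points

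| Risk by Day 112 | Entry (upa/dupi) | Upadacitinib | Dupilumab | Dupi − upa (points) |
|---|---|---|---|---|
| 50% | 0%/0% | 58.5% | 67.8% | 9.3 |
| 50% | 20%/40% | 56.8% | 60.7% | 3.9 |
| 50% | 30%/50% | 55.9% | 58.9% | 3.0 |
| 50% | 30%/60% | 55.9% | 57.1% | 1.2 |
| 50% | 30%/70% | 55.9% | 55.3% | −0.6 |
| 30% | 20%/40% | 35.1% | 38.5% | 3.4 |
| 10% | 20%/40% | 12.0% | 13.5% | 1.5 |
| 5% | 20%/40% | 6.0% | 6.8% | 0.8 |

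**Where the gap closes.** At p = 50% with 20% upadacitinib entry, solve 67.8 − f_d × 17.8 = 56.8. This gives f_d of about 62%; above that the sign reverses. In terms of mean window length, the gap closes at f_d = (41 + 30 f_u)/71, which is 58% to 70% for f_u between 0 and 30%.

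**With a common window** to Week 16 both arms count about 112 days, and equal risk gives a difference of 0.

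**The case against.** The windows have a stated reason. Protocol 7.5 defines treatment-emergent by five half-lives, and the SAP implements it. That stands: it justifies collecting and reporting the later events, and the 30/84-day tables should stay. It does not make percentages over unequal windows comparable.

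A reader might infer that 142 versus 183 days describes the whole of each arm, and so a fixed bias of some 3 to 4 points. The documents do not support that. The sentence that sets the tails also caps them at Period 2, and nothing in either document fixes the event rate or the share entering. A figure of 3 to 4 points is one assumed scenario among many.

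The calculation may also overstate the gap. SAP 2.2 and Protocol 5.6 waive the follow-up contact for subjects who start commercial upadacitinib or dupilumab at study completion or premature discontinuation. For the others, post-treatment follow-up is one scheduled contact, possibly by telephone, so later events may be recorded less completely. Both points stand and would shrink the difference by an unknown amount.

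The problem is partly handled already, because SAP 10.2.6 summarises AESIs to Week 16. That is right for those summaries. The overview in SAP 10.2.2 nevertheless lists AESIs among its TEAE categories, and the other TEAE rows have no common-window version.

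A reader might also count the absence of between-arm differences with confidence intervals for adverse events as a defect. No safety hypothesis is stated and Protocol 7.5 promises summaries, so that is a matter of preference and separate from the window.

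**Conclusion.** The concern holds for subjects who do not enter Period 2: the Period 1 TEAE window is about 41 days longer on dupilumab for on-schedule completers, and early discontinuers carry unequal tails. The planned percentages therefore compare arms over time at risk that depends on arm and on Period 2 entry, and the planned patient-year rates do not remove the distortion.

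Its size cannot be settled from the documents. Under the stated assumptions it is about 0 to 9 points, usually in upadacitinib's favour, smaller for rare events, and reversed when dupilumab entry into Period 2 is high enough. For scale, the 95% half-width for a difference at 50% with 440 per arm is 1.96 × √(2 × 0.25/440) = 6.6 points.

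One input needs reconciling. Day 99 follows SAP 6.0, but SAP 2.3 and Protocol 4.1 describe dupilumab dosing until the Week 16 visit. Read as a Day 113 dose, that would put the end of the window at 113 + 84 = Day 197.

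**What to change.** Keep the Protocol 7.5 windows (30 and 84 days) for the existing TEAE tables and listings. Add to SAP 10.2.2, 10.2.3 and 10.2.4, as the stated basis for comparing arms in Safety 1, percentages and rates over a common window:

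- Count events with onset from first dose to the earlier of the Week 16 visit and the day before Period 2 starts.
- For early discontinuers, use the scheduled Week 16 day in place of the visit, with one equal post-dose limit in both arms.
- Count patient-years over that same window, so that numerator and denominator match.
- State that the 30/84-day tables describe follow-up and are not for comparing arms.

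Also reconcile the wording on the last planned dupilumab dose between SAP 6.0, SAP 2.3 and Protocol 4.1.

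The cost is SAP wording and one more set of tables, with no new data. Later events would appear only in the 30/84-day tables. The equal post-dose limit departs from the five-half-life rule for at least one drug, which is acceptable because it applies to the comparison tables alone.

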5.3 Prohibited Medications and Therapy

Biologic Therapies

Current and concomitant biologic therapies and biosimilar versions of biologic drugs that are considered immune modulating (or immune suppressing) are prohibited during treatment with the study drug.

Subjects must have discontinued biologic therapies with immunosuppressive potential prior to the first dose of study drug as specified in the washout procedures (Eligibility Criterion 20, Protocol Section 5.1), OR at least five times the mean terminal elimination half-life of the medication prior to the first dose of study drug. No minimum washout prior to Baseline is required for a biologic therapy if an undetectable drug level measured by a commercially available assay is documented.

Biologic therapies with immunosuppressive potential are prohibited through the end of study drug administration, and include, but are not limited to, the following:

- Abatacept
- Adalimumab
- Anakinra
- Anifrolumab
- Belimumab
- Certolizumab
- Dupilumab
- Etanercept

- Golimumab
- Guselkumab
- Infliximab
- Ixekizumab
- Lebrikizumab
- Natalizumab
- Nemolizumab
- Risankizumab
- Rituximab
- Secukinumab
- Tocilizumab
- Tralokinumab
- Ustekinumab
- Vedolizumab

Other Non-Biologic Systemic Therapy

Concomitant treatment with systemic non-steroidal systemic immunosuppressive drugs is prohibited during treatment with study drug, including but not limited to:

- methotrexate
- cyclosporine
- azathioprine
- PDE4-Inhibitors (e.g., apremilast)
- mycophenolate mofetil

Oral antihistamines are allowed per investigator discretion for the duration of the study.

See also Section 5.4 for further details on allowed rescue.

Corticosteroids

Concomitant treatment with systemic corticosteroids (oral, intravenous, intramuscular) and intralesional corticosteroids for the treatment of AD is prohibited during treatment with study drug.

Inhaled, ophthalmic drops, and nasal corticosteroid formulations are allowed throughout the study.

Strong CYP3A Inhibitors or Inducers (includes over-the-counter or prescription medicines, vitamins and/or herbal supplements).

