7.5 Statistical Analyses for Safety

The safety analyses will be carried out using the Safety Population and will be based on treatments the subjects actually received. Safety will be assessed by AEs, physical examination, laboratory assessments, and vital signs. Note that missing safety data will not be imputed.

Adverse events will be coded using the Medical Dictionary for Regulatory Activities (MedDRA). Treatment-emergent adverse events (TEAEs) are defined as those that began or worsened in severity after the first dose of study drug and no more than 5 half-lives of the drug after the last dose of study drug. Specifically, 30 days will be used for upadacitinib, and 84 days (12 weeks) will be used for dupilumab. The number and percentage of subjects experiencing TEAEs will be tabulated using system organ class and preferred term, overall and by severity and by relationship to the study drug as assessed by the investigator by the Period using the Safety_1 population and Safety_2 population, respectively. Summaries (including percentages and events per 100 patient years) of TEAEs, AESIs, SAEs, deaths, and AEs leading to discontinuation will be provided in both Periods.

For laboratory tests and vital signs, mean change from baseline and percentage of subject with evaluations meeting pre-defined Potentially Clinically Important criteria will be summarized in both Periods. For selected lab parameters, a listing of all subjects with any laboratory value above Grade 3 of Common Toxicity Criteria will be provided. Additional details for the safety analysis will be provided in the SAP.

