**Table 1. Analyses Populations: ITT Populations and Safety Populations**

Analyses Populations	Study Period	Analyses Groups
ITT 1	Period 1	Dupilumab
		Upadacitinib a
ITT 2	Period 2	Upadacitinib/Upadacitinib 30 mg
		Dupilumab/Upadacitinib b
Safety 1	Period 1	Dupilumab
		Upadacitinib 15 mg c
		Upadacitinib a
Safety 2	Period 2	Upadacitinib/Upadacitinib 30 mg
		Dupilumab/Upadacitinib b
ALL UPA	During the upadacitinib administration	Upadacitinib 15 mg
		Upadacitinib 30 mg
		Any UPA d

- a. Upadacitinib subjects regardless of the dose level in Period 1.
- b. Dupilumab/Upadacitinib subjects regardless of the upadacitinib dose level in Period 2.
- c. Upadacitinib 15 mg subjects (who never received UPA 30 mg QD) in Period 1.
- d. Subjects who received at least one dose of upadacitinib regardless of the dose level in the study.

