### **During the administration of upadacitinib for All UPA Population:**

- For subjects who took UPA 15 mg QD, then escalate dose to UPA 30 mg QD, the number of planned tablets for UPA 15 mg QD will be used before dose escalation; the number of planned tablets for UPA 30 mg QD will be used after dose escalation, and the number of planned tablets of UPA 30 mg QD depends on the tablet types (15 mg or 30 mg depends on the site).
- For subjects who took UPA 15 mg QD and never experienced dose escalation, the number of planned tablets for UPA 15 mg QD will be used.

Dupilumab compliance is defined as the number of dupilumab injections administered during the subject's participation divided by the number of injections planned during the subject's participation in Period 1. The number of injections planned for dupilumab group in Period 1 is based on protocol Amendment 2.0, i.e., Week 14 dupilumab dose will be the last planned dose for all subjects in the dupilumab group if they complete Period 1.

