### **10.2.7 Adverse Events of Other Safety Topics of Interest**

Adverse Events of Other Safety Topics of Interest specifically for this study will be summarized by SOC and PT and listing format and will be based on standard or company MedDRA queries (SMQs or CMQs or selected PTs) in Period 1. Detailed information about the search criteria is provided in [Appendix G](#). The listings of Adverse Events of Other Safety Topics of Interest will be provided.

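### For dupilumab subjects who switch, the SAP ends the 84-day dupilumab event window at the switch, and ALL UPA then pools the 70-day overlap with subjects randomized to upadacitinib

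*SAP*

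**What the plan says.** - **Protocol 7.5** defines a treatment-emergent event by time since the last dose, "no more than 5 half-lives of the drug after the last dose of study drug", and turns that into days: "30 days will be used for upadacitinib, and 84 days (12 weeks) will be used for dupilumab". It also asks for tabulation by period.
- **SAP 10.2.1** ends the Period 1 window at the earlier of the drug-specific follow-up (84 days for dupilumab) and the day before Period 2. After that, "TEAEs in Period 2 are defined as any adverse events that begin or worsen in severity after initiation of upadacitinib in Period 2", up to 30 days past the last upadacitinib dose. A third definition, for events during upadacitinib administration, also starts at the first upadacitinib dose.
- **SAP 6.0** states that "Week 14 dupilumab dose will be the last planned dose for all subjects in the dupilumab group" if they complete Period 1. Exposure in Period 2 and in ALL UPA is counted in upadacitinib days only.
- **Protocol 4.1 and SAP 2.2** offer upadacitinib at Week 16 to dupilumab subjects below EASI 75. No interval between the two drugs is described beyond the normal injection spacing.
- **SAP Table 1** gives Safety 2 its own sequence group, footnoted as "Dupilumab/Upadacitinib subjects regardless of the upadacitinib dose level in Period 2". ALL UPA has three groups: upadacitinib 15 mg, upadacitinib 30 mg and any upadacitinib. None of them shows earlier dupilumab.
- **SAP 10.2.7** limits the grouped summary of other safety topics ("SMQs or CMQs or selected PTs) in Period 1") to the first period. Appendix G lists these topics, which include conjunctivitis, keratitis, helminth infection and arthralgia.

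**The concern.** The additional objective of the study is the efficacy and safety of upadacitinib after an inadequate response to dupilumab. By the protocol's own rule, an event within 84 days of the last injection can still belong to dupilumab. The SAP's cut means that, for a switcher, an event in that span counts as an upadacitinib-period event and is divided by upadacitinib exposure, and nothing marks the overlap.

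This matters most in ALL UPA. There an overlap event in a switcher cannot be told apart from an event in a subject who never had dupilumab on study, so the pooled rates mix upadacitinib with residual dupilumab. SAP 10.2.6 plans the AESI summaries for Baseline to Week 16 and for the whole upadacitinib treatment period, and the second of these appears to correspond to ALL UPA. Elsewhere the SAP treats the 84 days as meaningful without a cut: the death categories in 10.2.2 and the laboratory rule in 10.3 both use it.

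**Working it through.** **Inputs**
- Dupilumab window: 84 days (Protocol 7.5).
- Last planned dupilumab dose: Week 14 (SAP 6.0), which is Day 1 + 14 × 7 = Day 99.
- Week 16 = Day 113, Week 20 = Day 141, Week 32 = Day 225 (Protocol Appendix D).
- Tail of the Period 2 event window: 30 days (SAP 10.2.1).

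**Plan's own figure.** Protocol Appendix E describes the 12-week dupilumab follow-up as 2 weeks to the Week 16 visit plus 10 weeks after it. The study days give the same: 113 − 99 = 14 days, and 84 − 14 = 70 days = 10 weeks. The result does not depend on Appendix E.

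**Overlap**
- End of dupilumab window: 99 + 84 = Day 183.
- Overlap with Period 2: 183 − 113 = 70 days.
- Period 2 treatment: 225 − 113 = 112 days.
- Share of Period 2 treatment days: 70/112 = 62.5%.
- Share of the Period 2 event window with its tail: 70/(112 + 30) = 70/142 = 49%.

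**Sensitivity**

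| Case | Overlap | Share of 112 days |
|---|---|---|
| As planned | 70 days (10 weeks) | 62.5% |
| Switch visit 7 days early (assumed window) | 77 days (11 weeks) | 69% |
| Switch visit 7 days late (assumed window) | 63 days (9 weeks) | 56% |
| Week 14 dose missed, last dose Day 85 | 56 days (8 weeks) | 50% |
| Last dose at Week 16, Day 113 | 84 days (12 weeks) | 75% |

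The ±7 days is an assumption, because the visit-window row of Appendix D is broken in the text. The last row is there because Protocol 4.1 and SAP 2.3 describe dosing up to the Week 16 visit, which can be read as including a dose at that visit. That wording and SAP 6.0 should be reconciled.

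**Ceiling in ALL UPA.** Suppose all subjects complete, *s* dupilumab subjects switch and *u* upadacitinib subjects continue into Period 2. The share of pooled upadacitinib time inside the dupilumab window is then 70*s* / [112 × (440 + *s* + *u*)]. With *s* = 440 and *u* = 0 this is 70/224 = 31%. The real share is lower, since only subjects below EASI 75 who accept can switch. The documents project neither *s* nor *u*.

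**Efficacy visits.** Week 20 is 141 − 99 = 42 days after the last planned dose, inside the window. Week 32 is 225 − 99 = 126 days after it, outside.

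**The case against.** **The cut has a reason.** Protocol 7.5 itself requires tabulation by period, and the cut keeps one event from being counted in both. Treatment-emergent is a label of timing, not of cause, and investigator-assessed relatedness is tabulated separately. This stands, and it is why the cut should be kept. It does not answer the absence of any marker for the overlap.

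**The sequence is visible in Period 2.** A reader might infer that every table credits these events to upadacitinib alone. Safety 2 and ITT 2 show Dupilumab/Upadacitinib as a separate group, so that holds only for ALL UPA and for the event rule and denominator.

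**The events are tabulated.** A reader might infer from 10.2.7 that conjunctivitis, arthralgia and the like disappear after Week 16. SAP 10.2 and 10.2.3 tabulate all Period 2 events by SOC and PT, and 10.2.2 and 10.2.4 carry a line for these topics. Only the grouped topic-level breakdown is missing.

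**Section 5.3 is not contradicted.** A reader might set the direct switch against "Subjects must have discontinued biologic therapies with immunosuppressive potential prior to the first dose of study drug". That sentence governs washout before entry: it points to the eligibility criteria, and the same paragraph speaks of Baseline. Dupilumab is itself a study drug in Protocol Table 2, so its place on the prohibited list must mean use outside the study.

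**Residual drug cannot be quantified.** A reader might turn 84 days into a half-life and compute how much drug remains at Week 20. The documents give no half-life for dupilumab, only a follow-up window, so that figure would be an assumption.

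**Direct switching is the question asked.** The objective concerns subjects moved straight from dupilumab, so some carry-over belongs to the sequence under study. This stands for Safety 2. It does not justify pooling the same days with subjects who never received dupilumab on study.

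**Conclusion.** The concern holds as a matter of attribution and presentation. For a switcher on schedule, 70 of 112 Period 2 treatment days (62.5%; 49% of the event window with its tail) lie inside the window that the protocol assigns to dupilumab. The SAP counts events there only under upadacitinib. Safety 2 discloses the sequence but not the interval, and ALL UPA discloses neither.

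This rests on a Week 14 last dose, a Week 16 switch and full compliance. Across the cases tabulated, the share of treatment days runs from 50% to 75%. It concerns only dupilumab subjects below EASI 75 who accept the switch, and their number is not projected, so the effect on ALL UPA rates cannot be sized beyond the 31% ceiling.

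No hypothesis test is affected. Period 2 efficacy is descriptive, and the endpoints for switchers in Protocol 3.4 and SAP 3.3 are already defined at Week 32, outside the window. A reader might infer that Period 2 efficacy needs a new basis. It does not; only the Week 20 results need a label.

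**What to change.** Keep the period cut in SAP 10.2.1 and add the following:

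1. In SAP 10.2.1 and Table 1, also report events and patient-years of the Dupilumab/Upadacitinib group in two intervals: up to 84 days after the actual last dupilumab dose, and later. Split the exposure of SAP 6.0 at the same date.
2. In ALL UPA, show switchers and subjects randomized to upadacitinib in separate columns, plus the total.
3. Extend the grouped summary of SAP 10.2.7 to Period 2.
4. Footnote Week 20 efficacy in switchers as falling within the 84-day dupilumab window.

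The dosing and onset dates are already needed for the planned durations and event windows, so no new data are required and the primary analysis is untouched. The cost is SAP wording and a few more columns. The downside is smaller cells per interval, so rates for uncommon events will be imprecise and are best read beside the total.
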